#### **11.8.6 Prompt Reporting of SAEs**

All SAEs, whether or not considered related to the investigational product, must be reported within 24 hours of becoming aware of the event to the Medical Monitor listed on the second page of this protocol. The Medical Monitor will require the following patient information as listed on the SAE form:

- Subject identification, including patient study number, initials, and sex
- Date of first dose of investigational product
- Total dose and number of doses administered
- Date and amount of last dose of investigational product

- Whether the patient was taking investigational product at the time of the AE
- Date, duration, and description of AE
- Events and/or symptoms leading up to the AE
- Action taken, including whether patient was withdrawn from study
- Concomitant therapy (including doses, routes, and regimens)
- Pertinent laboratory data
- Medical history (including time on study prior to AE and history that might be related to the AE)
- Dosing status of investigational product (e.g., interrupted, discontinued, dose changed)

In addition to the above information, the Medical Monitor will require the investigator's assessment of the following:

- Intensity of the AE
- Investigator's assessment of the relationship of the AE to study treatment
- Outcome of the AE

Any necessary follow-up must be submitted within a reasonable time thereafter. The sponsor will promptly report SAEs to the FDA and other applicable regulatory agencies in accordance with Title 21 of the Code of Federal Regulations (CFR), Part 312.32 (21 CFR 312.32) and local regulatory requirements. The investigator should also comply with any applicable requirements related to the reporting of SAEs to the IRB/IEC.

The investigator will provide an SAE follow-up report to the sponsor. In this report, the investigator is to assess and record the SAE in detail, including the date and time of onset, description, intensity, duration, outcome, etiology, relationship to study drug, and action taken. Any SAEs that continue at the patient's last study visit must be followed until the event resolves or follow-up is agreed to be adequate by the investigator, Medical Monitor, and sponsor.

The clinical site investigator and the Medical Monitor will review each SAE report and evaluate the relationship of the SAE to study treatment and to underlying disease. Based on the investigator's and sponsor's assessment of the SAE, a decision will be made concerning the need for further action. The primary consideration governing further action is whether new findings affect the safety of patients participating in the clinical study. If the discovery of a new SAE related to vesigenurtacel-L raises concern over the safety of continued administration of study drug to patients, the sponsor will take immediate steps to notify the FDA and all investigators participating in clinical studies of vesigenurtacel-L.

Further action that may be required includes the following:

- Modification of the protocol
- Discontinuation or suspension of the study

- Modification of the existing consent form and informing current study participants of new findings
- Addition of any newly identified vesigenurtacel-L-related AEs to the list of expected AEs

## 12.0 STATISTICAL CONSIDERATIONS

### 12.1 General Statistical Considerations

#### Phase 1:

Data from Phase 1 of the study will be presented descriptively. Standard descriptive statistics will include the sample size, mean and standard deviation (SD), median, minimum, and maximum values for continuous variables. For categorical variables, the frequency of patients will be provided along with the percentage based on the number of patients with available data. Summaries will be based on observed data (i.e., no missing data will be imputed).

Analysis of the secondary efficacy parameters will follow the same approach as outlined for Phase 2 below.

#### Phase 2:

In Phase 2, the primary endpoint (proportion of patients alive and disease free at one year) between the two experimental groups and the control will be compared using Fisher's exact test and presented as odds ratios (OR) with 95% confidence intervals (CI) relative to the control group. For the statistical comparisons on the primary endpoint between the two experimental and control groups, there will be no adjustment for multiplicity. ORs will be generated with a simple logistic regression model with one year disease-free survival as the dependent variable and group as the sole independent variable (low dose and high dose vesigenurtacel-L vs. control). If the analysis of the primary endpoint does not suggest any dose response effect between the two vaccine arms, an exploratory analysis will be conducted where the two vaccine arms will be pooled and compared to the control arm for the primary endpoint (proportion of patients alive and disease-free at one year). The outcome will be presented as OR with 95% CI relative to the control group.

Efficacy comparisons between the monotherapy arm and any of the randomized arms will remain exploratory. However, safety and point estimates with appropriate measures of variance (SD, 95% CI) for the efficacy parameters for the fourth arm will be estimated.

The binary secondary endpoints will be presented as OR with appropriate 95% CI.

DFS will also be evaluated as a time to event endpoint, defined as disease recurrence or progression or death from any cause. For time to event endpoints, which will also include OS, time to cystectomy, and burden of repeat TURBT, survival curves will be generated by the method of Kaplan-Meier and compared with the log-rank test. In an exploratory analysis, the weighted log rank test will also be used. The weighted log rank preserves the statistical power that is lost due to the lag time effect in efficacy with immunotherapeutic agents.

Exploratory clinical and laboratory endpoints will be summarized descriptively by time point of collection. Statistical testing and CI will be provided as an aid in reviewing the collected data. A log10 transformation may be used as appropriate in order to determine 95% CI based on a t-test for the log-concentrations, and the bounds will be transformed back to the original scale for presentation purposes. Homogeneity between

treatment groups will be assessed using Wilcoxon rank-sum tests for numeric variables and Fisher's exact test for categorical variables.

An unblinded Interim Analysis may be performed when all randomized patients have completed the disease assessment at Week 25. The primary goal of this analysis will be to allow selection of a dose and dosing regimen for future manufacturing efforts. At the time of this analysis all patients will have been enrolled, and the outcome of this analysis will not impact continuation of the trial to the primary endpoint. The treatment assignment of individual patients will not be unblinded to physicians or patients.

All of the analyses will be performed using SAS® Version 9.1 (or later). Further details of the exact analysis methods can be found in the study-specific Statistical Analysis Plan.

## 12.2 Analysis Populations

Study populations are defined as follows

### Phase 1:

Safety Population: defined as all patients receiving at least one dose of vesigenurtacel-L

### Phase 2:

Intent-to-Treat (ITT): defined as all patients randomized into the study and who will be classified according to their assigned treatment group, regardless of the actual treatment received.

Safety Population: defined as all randomized patients who receive at least one dose of treatment (BCG, HS-410, or any combination thereof)

Per-protocol population: defined as all patients in the ITT population who do not have any major protocol deviations (including being non-compliant to the study drug)

Other sub-populations of patients for secondary and exploratory analyses may be defined at the time of statistical analysis and will be identified in any reporting of results.

Patients will be randomized to Arms 1-3 centrally using a stratified block design according to risk of recurrence (strata: high vs. intermediate risk) and CIS (strata: yes vs. no). The intent for stratification is to ensure balance between groups with respect to these important prognostic factors. Given the limited sample size, a formal subgroup analysis based on the stratification variables will not be undertaken. Patients who will not receive BCG will be consecutively allocated (non-randomized) into Arm 4 consisting of vaccine monotherapy.

Due to delays in the batch release of certain doses of vaccine, the randomization schedule may be temporarily revised from a 1:1:1 randomization to a 1:1 randomization, with one arm being briefly suspended. During the period of revised randomization, each patient will maintain at least a 50% chance of receiving vaccine versus placebo. Randomization strata will remain unchanged. Upon batch release of the vaccine the randomization will return to the original 1:1:1 ratio. In order to maintain the study blinding, temporary closure of certain arms will not be disclosed outside of the DMC except as needed for Informed Consent documents.

### **12.3 Accountability, Demographics, and Baseline Characteristics**

Accountability information will be summarized for each phase, including the number of enrolled patients, dosed patients, and patients who terminated at the first disease assessment, and the number of patients withdrawn by reason. Also, separately, the number of patients with recurrence events, dropping out, or continuing in the study will be summarized in order to show the percent of subjects without an event still being followed.

Descriptive information on demographics and baseline data including age, sex, weight, height, body mass index, physical examination, and medical history will be provided in a summary table. Summaries will be provided by treatment group and overall for the ITT and Per-Protocol population classifications.

### **12.4 Safety Analysis**

Safety analysis will be performed for the Safety Population in each phase of the study.

#### **12.4.1 Adverse Events**

Treatment emergent adverse events (TEAEs) will be defined as events that occur on or after the first dose of study medication. The Medical Dictionary for Regulatory Activities (MedDRA) coding dictionary will be used for the coding of AEs. TEAEs, serious or CTC Grade 3 or 4 TEAEs, and TEAEs related to therapy will be summarized overall and by system organ class and preferred term by treatment group. These will summarize the number of events and the number and percent of patients with a given event. A Fisher's exact test will be provided to evaluate if the number of patients with an event within a specific system organ class is homogeneous across the treatment groups. In addition, the number and percent of patients with TEAEs will be provided by maximum severity. A summary of all TEAEs by system organ class and preferred term occurring in at least 5% of subjects in either treatment group will be provided by quarter.

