### **3.3 Number of Subjects**

Approximately 110 patients will be enrolled from up to 20 clinical trial centers. In Phase 1, 10 patients will be enrolled in a single cohort given treatment with monotherapy low dose vesigenurtacel-L. In Phase 2, 25 patients will be enrolled in each of four arms: low dose vesigenurtacel-L in combination with BCG, high dose vesigenurtacel-L in combination with BCG, placebo in combination with BCG, and high dose vesigenurtacel-L monotherapy (100 patients total).

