#### **12.4.7 Safety of the Combination of Vesigenurtacel-L and BCG (Arms 1, 2, and 3 of Phase 2 Only)**

Safety is defined as the proportion of AE/SAE in patients receiving the combination of vesigenurtacel-L and BCG compared to the proportion of AE/SAE in patients receiving the combination of placebo and BCG.

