### **12.6.2 Phase 2**

For the randomized portion, a sample size of 75 subjects in the ITT population was selected for this study.

The sample size assessment was based on the following assumptions:

- 75 patients will be randomized to yield 69 evaluable (25 patients per arm)
- A one year disease-free survival rate of 60% in the control and 90% in the respective experimental groups for an absolute difference of 30% in favor of the experimental treatments
- 10% drop-out rate
- Type I error ( $\alpha$ ) = 0.10 and using a one sided test with no adjustment for multiplicity
- Power = 80% to detect a 30% difference in one year disease-free survival between the vesigenurtacel-L groups and the control group
- Patients are followed for three years after the last patient is enrolled

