The objective of the phase 2 study is to compare 1-year disease free survival of two doses of HS-410 + BCG versus BCG + placebo in patients with non-muscle invasive bladder cancer who have undergone TURBT. Given the phase 2 exploratory nature of the study, the overall level of significance will be 0.10, using a one sided test with no adjustment for multiplicity, 75 patients will be randomized in a 1:1:1 (low dose HS-410 plus BCG and high dose HS-410 plus BCG vs. plus BCG + placebo) ratio to yield 69 evaluable (23 patients per arm). 25 patients will be enrolled into the monotherapy arm. Under the assumption that the one-year disease-free survival rate in the control is 60%, the study will have an 80% power to detect a 30% absolute difference between the two experimental groups and the control. Patients will be followed for three years after the last patient has been enrolled and patients will be obtained from approximately 20 participating centers.

5 Statistical Considerations

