7.3 Exploratory Analyses

All primary and secondary efficacy endpoints will be reanalysed in the Per-protocol population.

If available in a suitable timeframe before reporting, immunologic response data will be listed in the CSR. If applicable, summaries and exploratory analyses will be specified in a separate analysis plan and presented in a separate report.

The following endpoints will be analysed:

- immunologic response of PBMCs,
- total PBMC counts by flow cytometry,
- evaluation of tumour tissue obtained from pre-treatment resection for antigen expression by immunohistochemical analysis,
- evaluation of tumour tissue obtained from repeat biopsy, if clinically indicated, for presence of infiltrating T-lymphocytes,
- T cell receptor sequencing of peripheral blood T cells before and during the course of treatment
- Tissue immune cell infiltration, and inflammatory cytokine levels in urine

8 Safety Analyses

Safety comparisons will be performed on all patients who received at least one dose of experimental treatment in both phases of the study. The safety variables to be analyzed include vital sign measurements, AEs, ECGs, routine hematology, coagulation factors, serum chemistry, urinalysis, and deaths. Unless otherwise noted, safety variables will be tabulated by descriptive statistics (n, mean, median, SD, minimum, and maximum; or n and percent) using the Safety Population. When calculating the incidence of adverse events, or any sub-classification thereof by treatment, time period, severity, etc., each subject will only be counted once and any repetitions will be ignored; the denominator will be the total population (or treatment group, as applicable) size. A descriptive summary of all Treatment emergent adverse events (TEAEs) by system organ class and preferred term will be provided.

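### The Fisher homogeneity test for adverse events in Protocol 12.4.1 conflicts with SAP 5.5 and does not estimate the vaccine-plus-BCG versus placebo-plus-BCG difference that Protocol 12.4.7 asks for

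*Protocol*

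**What the plan says.** Protocol 12.4.1 summarises treatment-emergent events by group: "These will summarize the number of events and the number and percent of patients with a given event". It adds breakdowns by seriousness, grade, relatedness and maximum severity. It then adds one inferential step: "A Fisher's exact test will be provided to evaluate if the number of patients with an event within a specific system organ class is homogeneous". The sentence closes with the words "homogeneous across the treatment groups". It does not name the arms, a significance level, a pairwise contrast or any conclusion that depends on the result. For laboratory values, vital signs, ECG and physical examination (12.4.2 to 12.4.4), the protocol plans no inferential comparisons.

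Protocol 12.4.7, headed for Arms 1, 2 and 3, sets the question: "Safety is defined as the proportion of AE/SAE in patients receiving the combination of vesigenurtacel-L and BCG compared to the proportion of AE/SAE in patients" on placebo plus BCG. It names no effect measure or interval. Protocol 12.4.6 treats Arm 4 separately, as numbers of events.

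SAP 5.5 restricts p-values to the primary comparison of the two doses with placebo, and promises point estimates with 95% confidence intervals for secondary endpoints. SAP section 8 says that "safety variables will be tabulated by descriptive statistics", and SAP 8.2 contains no Fisher test. Safety of the combination is a listed secondary endpoint in both documents (Protocol 3.4.2; SAP 2.1).

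**The concern.** There are three linked problems.

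1. The protocol provides a p-value that the SAP rules out.
2. The test does not match the question. An omnibus homogeneity test does not say which dose differs from placebo, in which direction, or by how much.
3. With 25 patients per arm, a non-significant result is compatible with a large excess of events in one dose arm, and a reader could take it as reassurance. This matters most for the dose of 1x10^7 cells, because Phase 1 gave only 1x10^6.

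It is also unclear which arms are tested. If Arm 4 were in the test, its lack of BCG could by itself produce a significant result, and that would say nothing about what the vaccine adds to BCG.

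**Working it through.** **Plan's own figure.** The documents give no power for the safety test. The one stated power is 80% for one-year disease-free survival (60% versus 90%, one-sided 0.10, 23 evaluable per arm in SAP section 4). Exact enumeration of the one-sided Fisher test gives 80.8%, so the method reproduces the plan's figure.

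**Inputs for the safety test.**
- Patients per arm: "In Phase 2, 25 patients will be enrolled in each of four arms" (Protocol 3.3). The safety population needs only one dose, so 25 is the natural number; 23 is shown as a check.
- Significance level: not stated. Assumed 0.05 two-sided, with 0.10 as a variant.
- Event rates: not stated. Assumed baselines of 5% to 20%, tripled in one dose arm.

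**Formula.** For counts x1, x2, x3 with total s, each table has conditional probability C(25,x1)·C(25,x2)·C(25,x3) / C(75,s). The Fisher (Freeman-Halton) p-value sums this over all tables with the same total that are no more probable than the observed one. The miss probability is 1 minus the sum, over all tables with p at or below alpha, of the product of the three binomial probabilities. This is a full enumeration, without simulation.

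**Three-arm test, tripling in one dose arm, 25 per arm:**

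| Assumed rates | Missed at 0.05 | Missed at 0.10 |
|---|---|---|
| 5% to 15% | 83% | 79% |
| 10% to 30% | 58% | 48% |
| 15% to 45% | 33% | 24% |
| 20% to 60% | 14% | 8% |

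At 23 per arm, 10% to 30% is missed 63% of the time at 0.05 and 50% at 0.10. A two-arm, two-sided test of one dose against placebo at 25 per arm misses 10% to 30% in 70% of trials at 0.05 and 55% at 0.10. Swapping the omnibus p-value for a pairwise p-value therefore does not help.

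**Worked example.** Take 1/25 (low dose), 5/25 (high dose) and 1/25 (placebo). The three-arm Fisher p-value is 0.20. High dose minus placebo is 0.20 - 0.04 = 0.16. The Wilson limits are 0.089 to 0.391 for 5/25 and 0.007 to 0.195 for 1/25. The Newcombe limits are:
- lower: 0.16 - sqrt[(0.200 - 0.089)^2 + (0.195 - 0.040)^2] = -0.03
- upper: 0.16 + sqrt[(0.391 - 0.200)^2 + (0.040 - 0.007)^2] = 0.35

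The p-value alone could be taken as reassuring. The interval shows that an excess of up to 35 points is not ruled out.

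**Is Arm 4 in the test?** Against inclusion: Protocol 12.2 defines the Phase 2 safety population as randomized patients who were dosed and calls Arm 4 non-randomized, and 12.4.6 and 12.4.7 keep Arm 4 apart from Arms 1-3. For inclusion: the Safety monitoring section of the synopsis counts everyone given at least one dose of study product. The wording of 12.4.1 does not settle it.

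**Four-arm test at 0.05, 25 per arm, no vaccine effect (one common rate in Arms 1-3):**

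| Assumed rate, Arms 1-3 | Assumed rate, Arm 4 | Rejects |
|---|---|---|
| 40% | 20% | 31% |
| 30% | 10% | 38% |
| 60% | 30% | 57% |
| 50% | 20% | 62% |
| 40% | 10% | 72% |
| 60% | 20% | 87% |

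With Arms 1-3 only and one common rate from this table, the three-arm test rejects about 4% of the time.

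**The case against.** The strongest reply is that the test carries little weight in the plan. It is provided beside counts, percentages and severity, no conclusion is tied to it, and neither the Data Monitoring Committee reviews (5.1.2) nor the stopping rules (5.2.2) use it. Protocol 12.1 refers to the SAP for the exact methods, and under SAP 5.5 no adverse-event p-value would be produced. All of this stands. A reader might infer that the protocol judges safety by whether this test is significant; the documents do not say so. What remains is that 12.4.1 still says the test will be provided, against the SAP.

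A second reply is that intervals are already promised: Protocol 12.1 gives odds ratios with 95% intervals for binary secondary endpoints, and SAP 5.5 gives estimates with intervals for secondary endpoints. It would therefore be too strong to say that no interval is planned anywhere. But neither passage names safety, and Protocol 12.4.1, 12.4.7 and SAP section 8 do not carry the promise out.

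A third reply is that the miss rates rest on assumed event rates. That is correct. System organ classes pool several terms, and injection-site reactions are expected (Protocol 11.6), so higher baselines, where the test does better, are plausible for some classes.

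Finally, intervals at this sample size contain no more information than the test. For 10% versus 30% the Wald half-width is 1.96 x sqrt(0.1 x 0.9/25 + 0.3 x 0.7/25) = 21.5 points. That stands too; the gain is that the uncertainty is shown.

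**Conclusion.** The point holds as a conflict between protocol and SAP, and as a mismatch between the test and the question in 12.4.7. A non-significant result would be weak evidence for uncommon events: under an assumed 0.05 and 25 per arm, a tripling in one dose arm is missed 83% of the time from a 5% baseline and 58% from 10%, but only 14% from 20%. A single miss rate of about 60% should not be quoted as general; it belongs to 10% to 30% at 0.05.

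A reader might also infer that Arm 4 is in the test and will make it reject. The documents do not support that. The randomized-only safety population and the split between 12.4.6 and 12.4.7 point the other way, and if Arm 4 were included, rejection would depend on the size of the BCG effect (31% to 87% in the cases run). The supported conclusion is that the arms are not named and the definitions disagree. This is a correction of wording and presentation; it does not affect the primary analysis.

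**What to change.** - Delete the Fisher sentence from Protocol 12.4.1, in line with SAP 5.5.
- In Protocol 12.4.7 and SAP 8.2, report each dose against placebo, in Arms 1-3 only, as a risk difference with a 95% score (Newcombe) interval. Do this at least for Grade 3 or higher treatment-emergent events, serious events, events leading to discontinuation, and each system organ class.
- State that lack of statistical significance will not be read as similar safety.
- Summarise Arm 4 separately with exact confidence intervals.
- Reconcile the safety-population definitions in the synopsis and Protocol 12.2 (repeated in SAP 5.2.2), so that the place of Arm 4 is explicit.

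The cost is wording in both documents and a few more table columns, with no new data or patients. The drawback is that wide intervals look less reassuring than a statement of no significant difference.
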